## Study Duration

The enrollment period for this study is expected to be approximately 6 months. The study will end when all patients have completed 12 months of treatment visit/follow-up from the initiation of the study drug, or when the last patient has expired, has been lost to follow-up, or has withdrawn consent, whichever occurs first. After the completion of this study, the Sponsor will continue providing ATG-010 to patients with clinical benefits (per Investigators' judgment) as needed, and continue collecting actively reported safety data.

## Study Drug, Dose and Administration:

ATG-010 will be given by oral administration at a fixed dose of 80 mg in combination with dexamethasone (20 mg) twice weekly for 4-week cycles. Try to take the medicine twice a week at a fixed time with dose interval of 48 hours (e.g., Monday and Wednesday or Tuesday and Thursday, etc). Dexamethasone 20 mg will be given with each dose of ATG-010. If some patients cannot tolerate dexamethasone 20 mg orally, the Investigator may decide to adjust the dexamethasone to a minimum of 10 mg for each dose in these patients. If patients still cannot tolerate this dose, a potential discontinuation or further dose reduction may be allowed by the Investigator after a discussion with the Sponsor's Medical Monitor. Dose modification of ATG-010 can be conducted based upon grade severity of the adverse events (AE) as per CTCAE version 4.03. If a patient experiences more than one AE, dose modification will be conducted based on the AE of highest severity. If drug-related toxicity requires a treatment delay of more than 28 days, the patient will be withdrawn from the study treatment. All dose modifications or treatment delays must be documented in the electronic case reporting form (eCRF) and reasons must be provided.

## Concomitant medications

To minimize nausea, unless contraindicated, all patients should receive 5-hydroxytryptamine (5-HT3) antagonists (e.g., palonosetron or equivalent) before the first dose of ATG-010, and the specific medication frequency should be adjusted according to the actual symptoms of the patients. Alternative anti-emetic agents may be used if the patient does not tolerate 5-HT3 antagonists. Additional anti-nausea and anti-anorexia agents may be given as needed (per National Comprehensive Cancer Network® [NCCN] Clinical Practice Guidelines® for Antiemesis, NCCN Clinical Practice Guidelines® for Palliative Care and Chinese Expert Consensus on Prevention and Treatment of Nausea and Vomiting Related to Anti-Cancer Drug Treatment [2019 version] ). Patients will also receive therapy as needed to mitigate ATG-010 side effects, as part of the best supportive care.

Blood product transfusions, antimicrobials, and growth factors including granulocyte

colony-stimulating factors (for neutropenia), erythropoietins (for anemia), and/or platelet-stimulating factors for (thrombocytopenia) as the best supportive care are also permitted.

Concurrent therapy with any other approved or investigational anti-cancer therapy is not allowed during study period. Patients are not allowed to participate in other clinical trials during the study.

## Study Endpoints

### Primary endpoint

Overall response rate (ORR): Proportion of patients who achieve stringent complete response (sCR), complete response (CR), very good partial response (VGPR), partial response (PR).

### Secondary endpoints

#### a. Efficacy:

- Survival rate (SR) at 6 months, 9 months, and 12 months
- Time to progression (TTP): Duration from start of study treatment to time of disease progression
- Progression-free survival (PFS): Duration from start of study treatment to PD or death (regardless of cause), whichever comes first
- Duration of response (DOR): Duration from the first observation of at least PR to time of disease progression, or deaths due to disease progression, whichever occurs first
- CBR: Proportion of patients who achieve sCR, CR, VGPR, PR, or minimal response (MR)
- DCR: Proportion of patients who achieve sCR, CR, VGPR, PR, MR, or stable disease (SD; for a minimum of 12 weeks)
- OS (Kaplan-Meier estimates)
- MRD in patients who achieve CR and sCR
- The effect of risk factors stratification based on fluorescence in situ hybridization (FISH) on clinical efficacy, including del 13, del 17p13, t(4;14), t(14;16), 1q21 amplification

#### b. Safety and tolerability

#### c. PK: including but not limited to ATG-010 Cmax and tmax

### Criteria for Treatment Discontinuation:

At the discretion of the Investigator, patient study treatment could be discontinued for any of the following reasons and the Investigator will make the decision after timely communication with the clinical trial monitor under specific circumstances:

- Disease progression,
- Intolerable AE(s),
- Patient decides to discontinue study therapy or withdraws consent,
- Inappropriate to continue study participation by the Investigator or significant protocol violation in the opinion of Investigator and Medical Monitor.

Patients may decide to discontinue study treatment for any reason. Patients who elect to discontinue study treatment should be encouraged to continue in the study by Investigator so that the follow-up information on disease progression and survival status may be obtained. However, patients may elect to withdraw consent and decline further participation in the study. In this situation, the reason for discontinuation should be clearly documented by Investigator. Supportive clinical data are required when disease progression is confirmed. If the patient is removed from the study by request from Investigator, the reason for withdrawal should also be documented.

## Statistical Summary

Primary analysis (including efficacy, safety, and PK) will be conducted at 3 months after the last patient enrollment. Supplementary efficacy and safety analysis will be conducted after the completion of the study.

An interim analysis will be performed when approximately 50 patients have completed the clinical efficacy evaluations to assess the distribution of the patients who had previously received RRMM treatment. During interim analysis, the clinical efficacy in patients who had previously received 3 types of drugs (at least an immunomodulatory [i.e., lenalidomide], at least a protease inhibitor [i.e., bortezomib], and at least an anti-CD38 antibody) should be analyzed, but the efficacy of whole population enrolled will not be analyzed.

## Sample Size Justification

This is a bridging study. A sample size of 82 patients will allow 80% power to detect a statistical significance with the target ORR of 28% against the threshold ORR of 15% (one-sided  $\alpha=0.025$ ).

## Efficacy Evaluation

The primary efficacy analysis will be based on the ORR (proportion of patients who achieve sCR, CR, VGPR, or PR) as assessed by an independent review committee (IRC) using the modified intent-to-treat (mITT) population, defined as patients who receive at least 1 dose of study treatment. Supportive analysis of ORR will be performed using the per-protocol (PP) population.

A PP population will consist of all patients in the mITT population who meet the following criteria:

- Have ATG-010 dosing compliance  $\geq 70\%$ ,
- Have at least 1 complete post-baseline response assessment unless death or study withdrawal from the clinical trial,
- No major protocol violations that would compromise the assessment of efficacy. The list of major protocol violations that affect statistical analysis will be finalized before database lock.

Secondary efficacy endpoints include: PFS, TTP, CBR, DOR, etc. They will be assessed using the mITT and PP population. Time to failure event with censored value (including PFS, TTP, DOR) will be assessed for overall survival using Kaplan-Meier methods. The 95% confidence interval will be provided for ORR and CBR.

## PK evaluation

The pharmacokinetic parameters of ATG-010 will be calculated from the plasma concentration data with non-compartment model. Descriptive statistics will be provided for all concentration data and PK parameters.

## Safety Evaluation

Data from all patients who take at least one dose of study drug will be used for safety analysis of study drug. All AEs will be coded using the Medical Dictionary for Regulatory Activities (MedDRA). AEs will be graded by CTCAE version 4.03 and AE frequency will be tabulated by MedDRA term and system organ class.

A patient that experiences the same AE more than once will be counted only once. Other safety assessments such as hematology and chemistry will also be analyzed in the safety population.

**Table 1: Schedule of Assessments and Study Activities**

Activity/Assessment	Screening	Cycle 1					Cycle 2				Cycles ≥ 3	End-of-Treatment (EoT) Visit	Safety Follow-up Call	Survival Follow-up 
	Day -21 to Day -1	Day 1	Day 3	Day 8	Day 15	Day 22	Day 1	Day 8	Day 15	Day 22	Day 1	≤ 14 Days Post Last Dose	30 Days Post Last Dose	Every 3 moths
		-1 days	+ 1 days	±1 days	±1 days	±1 days	±2 days	±2 days	±2 days	±2 days	±2 days		+ 7 days	±14 days
Informed consent	X													
Inclusion/exclusion criteria	X													
Demographics	X													
Medical history 	X	X												
Patient height	X													
Patient weight	X	X		X	X		X		X		X	X		
Physical examination, including vital signs 	X	X		X	X		X		X		X	X		
ECOG scoring 	X						X				X	X		
Echocardiogram or MUGA 	X													
12 Lead ECG 	X											X		
Clinical Laboratory														
Urinalysis 	X											X		
Hematology 	X		X	X	X	X	X	X	X	X	X			
TSH 	X											X		
Complete serum chemistry 	X						X				X	X		
Limited serum chemistry			X	X					X					
Coagulation tests 	X											X		
HBV, HCV, HIV 	X					(X)					(X)			
Serum hCG pregnancy test 	X					X (D1 of each cycle only)					X (D1 of each cycle only)	X		
C-reactive protein	X					X					X	X		

**Table 1: Schedule of Assessments and Study Activities (Continued)**

Activity/Assessment	Screening	Cycle 1					Cycle 2				Cycles ≥ 3	End-of-Treatment (EoT) Visit 	Safety Follow-up Call	Survival Follow-up 
	Day -21 to Day -1	Day 1	Day 3	Day 8	Day 15	Day 22	Day 1	Day 8	Day 15	Day 22	Day 1	≤ 14 Days Post Last Dose	30 Days Post Last Dose	Every 3 months
		-1 days	+ 1 days	±1 days	±1 days	±1 days	±2 days		+ 7 days	±14 days				
Multiple Myeloma Assessments														
SPEP and serum protein immunofixation 	X	X					X				X	X		X
UPEP (24-hr urine for total protein) and urine protein immunofixation 	X	X					X				X	X		X
Quantitative Ig levels 	X	X					X				X	X		X
Serum FLC 	X	X		X			X		X		X	X		X
β2-microglobulin	X											X		
Skeletal survey 	X					(X)					(X)	X		(X)
Plasmacytoma assessment 	X					(X)					(X)	X		(X)
Bone marrow aspirate 	X					(X)					(X)			(X)
Bone marrow biopsy 						(X)					(X)			
Myeloma Assessment	X					X					X	X		(X)
PK Sampling 		X		X										
Study drug dosing		ATG-010 80 mg + dexamethasone 20 mg (both twice weekly), oral, 4-week a cycle												
Adverse events 	X	X	X	X	X	X	X	X	X	X	X	X		
Concomitant medications	X	X	X	X	X	X	X	X	X	X	X	X		
Telephone contact 			X										X	X
Antineoplastic therapy after EoT												X	X	X

(X) indicates that additional information is provided in the footnotes. Merged cells indicate that the procedure may be performed during either Screening or C1D1 visit prior the first dose of study drug.

Abbreviations: sCR = stringent complete response; CR= complete response; ECG = electrocardiogram; ECOG = Eastern Cooperative Oncology Group; EoT = End of Treatment; Ig = immunoglobulin; MM = multiple myeloma; MRD= minimal residual disease; SPEP = serum protein electrophoresis; UPEP = urine protein electrophoresis; CBC = complete blood count; FLC = free light chain.

- 1 Including details of all prior anti-myeloma therapies. Includes baseline symptoms as well as a detailed history of prior cancer therapies, especially MM therapies, including start and stop dates, disease progression during or after therapy, as well as discontinuations due to intolerance or any other serious illness.
- 2 Complete physical examination (PE) during Screening and EoT visit. Limited PEs during the study should be symptom directed. All PEs include vital signs (blood pressure, pulse, respiratory rate, and body temperature).
- 3 The following procedures may be performed at Screening or prior the first dose of study drug on C1D1 visit and as shown in the Schedule during the study: ECOG score, echocardiogram or MUGA scan, 12-lead ECG, urinalysis, hematological tests, TSH, complete serum chemistry, coagulations tests, and infectious disease tests. ECG should be performed whenever there are clinical indications.  
Hematology labs: Weekly for Cycles 1-2. During Cycle 1, hematology labs will be performed at each study site on Days 1, 8, and 15, and locally on Day 22; during Cycle 2, hematology labs will be performed at each study site on Days 1 and 15, and locally on Days 8 and 22. If the screening hematology test is performed within 5 days prior to Cycle 1 Day 1, it does not need to be repeated on Cycle 1 Day 1. If hematology test is required on Cycle 1 Day 1, it should be clarified that this hematology test result meets the protocol inclusion criteria before the first dose.
- 4 Viral serology is performed at Screening, including HBsAg, HBsAb, HBcAb, HBV-DNA (eg, negative for HBsAg and positive for HBcAb), HCVAAb, HCV-RNA (eg, positive for HCVAAb), and HIV. If HBsAg is negative but anti-HBc is positive at screening, HBV-DNA must be tested and then repeated once every subsequent cycle (i.e., every 4 weeks).
- 5 For females of childbearing potential; negative serum hCG pregnancy test must be obtained within 3 days before the first dose of study treatment. Pregnancy testing (serum hCG or urine) is also required for females of childbearing potential prior to dosing on Day 1 of Cycles  $\geq 2$  and at the EoT Visit (serum hCG). Pregnancy testing may also be performed as clinically indicated during the study.
- 6 Response criteria include SPEP, UPEP, serum and urine immunofixation, quantitative Ig levels, and serum FLC assay on C1D1 and must be taken on prior of the first dose of study drug. The assessments must be repeated on the first day of following cycle, at the time of disease progression or suspected response in order to confirm response. Note: For patients who achieve CR or sCR, as assessed by the local laboratory, portions of collected samples will be shipped to the central laboratory for further confirmation.
- 7 Skeletal survey to be performed using x-rays per institutional guidelines. If x-rays are used, they should include a lateral radiograph of skull, anteroposterior and lateral views of the spine, and anteroposterior views of the pelvis, ribs, femora, and humeri. If clinically appropriate, MRI, CT, or PET/CT, with tumor measurements, may be

Confidential

02 Jan 2020, v4.0  
(02 Dec 2020 translated)

14/84

used instead of, or in addition to, x-rays. If bone lesions or plasmacytomas are observed at baseline, their number and size should be recorded in the CRF. Bone lesions and/or plasmacytomas seen at baseline using imaging should be assessed as clinically appropriate per Investigator's discretion during the study. Skeletal survey results will be judged by the radiologist at the local laboratory.

8 If plasmacytomas are detected at baseline by PE, they should be measured and recorded, and re-assessed during the PE on Day 1 of each cycle, EoT visit, and every 3 months (if clinically appropriate) during follow-up.

9 Bone marrow aspirates:

- a. At Screening for karyotyping and FISH analysis to confirm diagnosis and classify MM sub-type (required per standard of care).
- b. MRD analysis at response for CR, sCR, or potential CR in patients with FLC only or unequivocal immunofixation electrophoresis (IFE).
- c. Efficacy assessment is performed according to the guidelines of the International Myeloma Working Group (IMWG).

10 Bone marrow biopsies:

- a. Validation of CR and sCR by the central laboratory in accordance with the guidelines of the International Myeloma Working Group (IMWG) (the levels of SPEP, UPEP, FLC, and quantitative Ig should be confirmed as soon as they are known).

11 PK sampling timepoints refer to Section 9.5.1.

12 All serious adverse events that occur after patient signs the ICF (including prior to first dose) and the adverse events that occur after the first dose of (including serious adverse events).

13 Telephone call (or visit) with patient to evaluate supportive care medications, concomitant medications and adverse events, and to adjust supportive care as appropriate. The telephone contact with the patient must take place on C1D3 (following administration of first dose of ATG-010 on C1D1). Survival follow up should be conducted via telephone call or in-person contact with the subject every 3 months until death or study discontinuation. MM disease status, survival, subsequent antineoplastic therapy, and drug-related SAE data will be collected at these phone calls/visits.

14 The end of treatment (EoT) visit is considered to be  $\leq$ 14 days after the last medication, and if it is more than 14 days after the last medication, the EoT visit will be performed within 1 week when the Investigator judges that the subject has permanently terminated the study drug.

15 After treatment discontinuation, if possible, for patients who are not progressing, SPEP with serum immunofixation, UPEP (24 h) with urine protein immunofixation, serum FLC, and quantitative Ig levels should be performed every 3 months for 1 year to assess durability of response.

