### 7.2. Independent Review Committee

The Independent Review Committee (IRC) will review the disease assessment data and independently assess the disease response. Disease response assessed by IRC is the basis for the evaluation of primary endpoint.

The IRC membership, functions, and procedures (including resolving the disagreements with the Investigators regarding disease assessment) will be stipulated in the *IRC Charter*.

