## 9.2. MM disease specific assessments

Patient response is assessed according to the procedures summarized in Table 4 and staged according to the IMWG response criteria summarized in Table 10 (Appendix 3). Disease response will be uniformly assessed by the independent IRC (Section 7.2).

According to IMWG, the quantitative Ig level measured by nephelometry can be used to replace the M-protein level measured by SPEP for patients with IgA or IgD myeloma. Besides, if a patient fails to provide the 24-hour urine sample after screening, the response profile will be confirmed per IMWG. At each study visit, all MM assessments specified in this study protocol should be carried out prior to dosing. If MM assessments are performed at unscheduled times, these results must be recorded as unscheduled visits in the eCRF. These assessments include SPEP, UPEP, serum FLC,  $\beta$ 2 microglobulin, quantitative Ig, and serum/urine protein immunofixation.

The results of SPEP and serum protein immunofixation, quantitative Ig, serum FLC, and 24-hour UPEP with immunofixation must be recorded at each specified time point. A blood sample and a urine sample will be sent to the central laboratory at each time point. If the central laboratory results show achievement of CR or sCR, samples for subsequent MM disease assessment should be collected per IMWG and sent to the central laboratory for confirming the CR or sCR. At each time point, approximately 12.5 mL of blood and 24-hour urine should be collected and sent to the central laboratory. For detailed information, please refer to the Laboratory Manual.

No matter what kind of diagnosis is currently adopted (for example, 24-hour UPEP must be collected at each time point specified in the study protocol, even though SPEP, Ig, or FLC is currently adopted for the patient), all diseases assessment (SPEP, UPEP, FLC, quantitative Ig, and serum/urine protein immunofixation) should be performed.

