**Table 4: Special Assessments of MM**

Procedure	Notes
SPEP and serum M-protein level determination	Per IMWG.
UPEP (24-hr urine for total protein) and urine M-protein level determination	Per IMWG. If a patient fails to provide the 24-hr urine sample, it should be recorded. Every effort should be made to collect 24-hr urine samples at the specified time points. The 24-hour urine sample collected must be performed with UPEP - other methods are not acceptable. UPEP must be performed at each time point specified in the study protocol, even if SPEP is adopted for the patient.
Serum FLC	Per IMWG.
Quantitative Ig level	Per IMWG. For IgA myeloma and IgD myeloma, quantitative Ig determination is preferred for disease assessment; the same variation rate should be adopted for serum M peaks. Only nephelometry can be used for response assessment, and SPEP and nephelometry value cannot be used interchangeably. (Durie et al., 2006).
$\beta$ 2 microglobulin	For MM staging (Appendix 2), not for response assessment (for the local laboratory only)
Skeletal survey	Skeletal survey (by X-rays and/or other clinically appropriate imaging methods [MRI,

Procedure	Notes
	
whole body CT, or PET/CT]) will be performed per Investigator's discretion within 45 days prior to C1 D1, and if clinically indicated, may be performed per Investigator's discretion during the study period. X-rays should include a lateral radiograph of skull, anteroposterior and lateral views of the spine, and anteroposterior views of the pelvis, ribs, femora, and humeri.
 
The results will be interpreted by the local laboratory.
 
If lytic bone lesions or plasmacytomas are observed at Screening, their number and size should be recorded in the CRF. Bone lesions and/or plasmacytomas seen at baseline should be assessed during the study period by the same imaging method adopted at screening, with the assessment frequency determined per Investigator's discretion.
 
 
For patients without soft tissue plasmacytomas (i.e., bone lesions only), skeletal survey should be performed by X-rays or low-dose CT. Contrast radiography is not required.
 
For patients with soft tissue plasmacytomas, skeletal survey should be performed by X-rays or low-dose CT (contrast radiography not required) and MRI or CT or PET/CT should be additionally performed, for which contrast enhancement is often required.
 

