### 9.2.3. Bone Marrow Biopsy for Efficacy Confirmation

This will be performed as soon as possible after confirmation of CR and sCR based on serum and urine assessments (per IMWG). If serum and urine immunofixation is negative and any soft tissue plasmacytoma disappears, a tissue core biopsy must be performed to confirm CR and sCR. For more information about these procedures, please refer to the Laboratory Manual.

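### Do Table 1 footnote 6 and Section 9.2 conflict on whether a local or a central result starts CR/sCR confirmation, and does that leave the ORR open?

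*Combined protocol and SAP*

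**What the plan says.** **Trigger and shipment.** Table 1 footnote 6 lists the response tests, requires them to be repeated to confirm a suspected response, and closes with a Note that reads: "For patients who achieve CR or sCR, as assessed by the local laboratory, portions of collected samples will be shipped to the central laboratory". The stated purpose is a second check of the response. Section 9.2 says "A blood sample and a urine sample will be sent to the central laboratory at each time point". Its next instruction is: "If the central laboratory results show achievement of CR or sCR, samples for subsequent MM disease assessment should be collected per IMWG". Those later samples also go to the central laboratory, so that the response can be confirmed.

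**Steps that follow a CR/sCR.** Footnote 10 describes the biopsy as "Validation of CR and sCR by the central laboratory in accordance with the guidelines", meaning those of the International Myeloma Working Group (IMWG). Section 9.2.3 says of the biopsy: "This will be performed as soon as possible after confirmation of CR and sCR based on serum and urine assessments", without naming a laboratory. Footnote 9b asks for "MRD analysis at response for CR, sCR, or potential CR in patients with FLC only" or with an immunofixation condition.

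**Primary endpoint.** Section 7.2 says "Disease response assessed by IRC is the basis for the evaluation of primary endpoint" and leaves the committee's functions and procedures to the IRC Charter. Section 13.3.3 bases the primary ORR on the IRC read and adds an investigator-assessed ORR. Neither section says whether the IRC reads local or central SPEP, UPEP, immunofixation, free light chain (FLC) and immunoglobulin values. Table 4 describes beta-2 microglobulin as "not for response assessment (for the local laboratory only").

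**The concern.** Read side by side, one passage starts from a local result and the other from a central one. One speaks of portions of samples already collected, the other of samples from later assessments. Footnote 6 mentions no other central shipment, so a site working from the schedule table alone might think samples go to the central laboratory only after a local CR/sCR. That site could then lack a central baseline.

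The second worry concerns the primary endpoint. If local and central values both exist and neither is named as governing, the choice could in principle be made after results are known. The trial is open-label and reports both an IRC and an investigator ORR. The test also turns on a single responder, so a patient classed as PR by one laboratory and MR by the other could in principle decide it.

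**Working it through.** **1. Can both passages be followed?** Section 9.2 sends samples centrally at every time point. Footnote 6 sends portions centrally when the local laboratory sees CR/sCR, and does not say that this is the only occasion.

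- Local CR/sCR seen first: samples go to the central laboratory, which then produces the central result on which Section 9.2 acts.
- Central CR/sCR without a local one: Section 9.2 applies directly.

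The rules work as a sequence, and footnote 10 places validation centrally either way.

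**2. Confirming material.** The sentence before the Note requires repeat assessments to confirm response, so the collected samples can include the repeats. Section 9.3 requires two consecutive samples, which may be drawn on the same day if analysed independently. Table 10, footnote 1, likewise requires two consecutive assessments. Both wordings fit this rule.

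**3. Effect of the trigger on ORR.** ORR counts sCR, CR, VGPR and PR. A patient not confirmed as CR who still meets VGPR or PR remains a responder, so ORR changes by 0 patients.

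How many patients could the trigger touch at all? Section 4.2.2 reports 2 sCR and lists no CR among 122 patients in STORM Part 2:

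- 2/122 = 1.64%, exact 95% interval 0.20% to 5.80%
- 82 × 1.64% = 1.3 patients; range 82 × 0.20% = 0.2 to 82 × 5.80% = 4.8

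Using the STORM rate here is an assumption. Section 8.2 sets a minimum prior exposure and no maximum number of lines, so the documents do not show whether this trial's rate would be higher or lower. For MRD, Table 10, footnote 1, starts testing at suspected CR and does not require two assessments, so that step does not wait for a settled confirmation.

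**4. Which laboratory the IRC uses.** The passages that bear on this point one way:

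| Place | Laboratory |
|---|---|
| Section 9.2, response blood and urine | central, every time point |
| Section 9.4.2, safety tests | local |
| Section 11.1.4, extra monitoring after dose reduction in patients with at least VGPR | local permitted |
| Table 4, beta-2 microglobulin (not a response marker) | local |
| Table 4 and footnote 7, skeletal survey | read locally |

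Where the plan wants local analysis, it says so. Response samples are the ones it sends centrally.

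**5. How near the ORR decision is.** The plan's figure is 80% power with 82 patients, 28% against 15%, one-sided 0.025 (Section 13.1.2). By exact binomial with success at 20 or more responders:

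- P(X ≥ 20 | n = 82, p = 0.15) = 0.0172
- P(X ≥ 20 | n = 82, p = 0.28) = 0.8012

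The stated power is reproduced. One patient is 1/82 = 1.2 points. Lower 95% bounds against the 15% threshold:

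| Responders | Clopper-Pearson | Wilson |
|---|---|---|
| 18 | 13.56% | 14.36% |
| 19 | 14.56% | 15.37% |
| 20 | 15.58% | 16.38% |

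The boundary lies between 19 and 20 under Clopper-Pearson and between 18 and 19 under Wilson. Section 13.3.3 names no interval method; the exact one matches the planned power. If the true ORR is 28%, the chance of landing on 19 or 20 is P(X ≥ 19) − P(X ≥ 21) = 0.8647 − 0.7234 = 0.14. That is the chance of sitting at the edge, not of a changed conclusion. A change would also need laboratory discordance at the PR/MR boundary in the deciding patient, and the documents give no discordance rate.

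**The case for a change.** The strongest contrary case is that two current passages describe the trigger differently and no third passage reconciles them. If central samples already go at every visit, a separate shipment after a local CR/sCR has no obvious purpose, which suggests that the footnote describes a different arrangement. A site following the table alone could fail to send a central baseline, and a central percentage change could then not be calculated for that patient. Section 7.2 does not list the laboratory source among the Charter's contents, and the protocol nowhere ranks the two sets of values. Alignment would cost a few sentences.

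The difference in wording stands, and so does the absence of an explicit statement of source. The inferred harm does not. Reading the footnote as permitting central shipment only after a local CR/sCR adds a restriction that is not in the text. A site that omits routine central samples departs from an explicit instruction in Section 9.2, which is a matter of conduct rather than a defect in the analysis. Procedures for committee review and sample handling are the normal content of a charter and a laboratory manual, and the protocol cites both. Section 13.3.3 already makes the IRC read primary and the investigator read additional.

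**Conclusion.** No change to the plan is needed. The difference between footnote 6 and Section 9.2 is a clerical one: both can be followed together, both lead to central confirmation, and the effect on ORR is 0 patients. At most, the timing of CR/sCR confirmation, biopsy and MRD sampling is unclear for about 1.3 of 82 patients (0.2 to 4.8), assuming the STORM Part 2 rate carries over. The unnamed source of the IRC's values is a detail that analysts and the committee would sensibly fill with the central results Section 9.2 already collects. Nothing in the plan, if followed, yields a wrong ORR.

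This rests on two assumptions: that sites follow Section 9.2 on central shipment, baseline included, and that the IRC Charter or the Laboratory Manual, neither of which was available here, does not contradict it. If the committee were in fact given a mixture of local and central values, the question would concern that document, and its reach would be limited to patients at the PR/MR boundary.
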